2.2 Secondary Objectives

- To assess the change in CD8+ TIL density from pre-treatment Transurethral Resection of Bladder Tumor (TURBT) to post-treatment Radical Cystectomy (RC) tissues separately in patients treated with nivolumab or combination of nivolumab/lirilumab.
- To assess percentage (%) change in CD8+ TIL density from pre-treatment TURBT to post-treatment RC tissues separately in patients treated with nivolumab and combination of nivolumab/lirilumab.
- To describe the rate of patients in each cohort who do not get RC within 6 weeks after completion of neoadjuvant treatment specifically and directly related to treatment-related adverse events (AEs).
- To assess the antitumor efficacy of nivolumab and combination of nivolumab/lirilumab as measured by pathologic complete (pT0N0) and partial (<pT2N0) response rate in the two cohorts.
- To assess the rate of recurrence-free survival (RFS) at the two-year time point from the time of registration in patients treated with nivolumab and combination of nivolumab/lirilumab.

2.3 Exploratory Objectives

- To assess the prognostic and predictive value of the expression of baseline immunohistochemistry (IHC) markers of interest (e.g. PD-1, PD-L1, PD-L2, NKG2D, KIR2DL1/2/3), and change in expression, for pathologic partial and complete tumor response (defined by cystectomy pathologic staging <pT2N0 and pT0N0, respectively), in patients treated with nivolumab and combination of nivolumab/lirilumab.
- To assess the prognostic and predictive value of peripheral blood mononuclear cell (PBMC) T-cell subset status (%CD4+ T-cells, %CD8+ T-cells, %T_{reg} T-cells, %Myeloid Derived Suppressor Cells, %Natural Killer cells, etc.) and change in status, as assessed by flow cytometry analysis, for pathologic partial and complete tumor response (defined by cystectomy pathologic staging <pT2N0 and pT0N0, respectively), in patients treated with nivolumab and combination of nivolumab/lirilumab.
- To compare CD8+ TIL density in post-treatment RC tissues in patients treated with nivolumab and combination of nivolumab/lirilumab.
- To assess the prognostic and predictive relationship between pre- and post- treatment TIL and NK-cell level and activation and pathologic partial and complete response (defined by cystectomy pathologic staging <pT2N0 and pT0N0, respectively) as well as two-year RFS, in patients treated with nivolumab and combination of nivolumab/lirilumab.
- To assess impact of prior BCG exposure on rates of pathologic partial and complete response (defined by cystectomy pathologic staging <pT2N0 and pT0N0, respectively) as well as two-year RFS, in patients treated with nivolumab and combination of nivolumab/lirilumab.

- To assess the prognostic and predictive relationship of tumor mutational load, neo-epitope burden, intrinsic molecular subtypes (basal vs. luminal), and T-cell clonality with pathologic partial and complete response (defined by cystectomy pathologic staging <pT2N0 and pT0N0, respectively) as well as two-year RFS, in patients treated with nivolumab and combination of nivolumab/lirilumab.
- To assess the prognostic and predictive relationship of pre- and post-treatment peripheral blood T-cell subsets, CD4+/CD8+ and CD4+/FOXP3+ ratios and plasma cytokine multiplex panels with pathologic partial and complete response (defined by cystectomy pathologic staging <pT2N0 and pT0N0, respectively) as well as two-year RFS, in patients treated with nivolumab and combination of nivolumab/lirilumab.
- To assess the prognostic and predictive relationship between pre- and post-neoadjuvant treatment levels in plasma cytokine biomarkers of interest (e.g. IFN- α , TGF- β , IL-10, IL-4, IL-5, IL-13, IFN- γ , etc.) and pathologic partial and complete response (defined by cystectomy pathologic staging <pT2N0 and pT0N0, respectively) as well as two-year RFS, in patients treated with nivolumab and combination of nivolumab/lirilumab.
- To assess prognostic and predictive associations between baseline tumor and/or tumor infiltrating lymphocyte tissue and ctDNA genomic alterations, gene expression, and methylation signatures for pathologic partial and complete response (defined by cystectomy pathologic staging <pT2N0 and pT0N0, respectively) as well as two-year RFS, in patients treated with nivolumab and combination of nivolumab/lirilumab.
- To assess prognostic and predictive value of serum circulating antibody profiles on pathologic partial and complete response (defined by cystectomy pathologic staging <pT2N0 and pT0N0, respectively) as well as two-year RFS, in patients treated with nivolumab and combination of nivolumab/lirilumab.
- To assess CD8+ TIL density by central pathology review using image analysis in both cohorts.

3. Selection of Patients

Each of the criteria in the checklist that follows must be met in order for a patient to be considered eligible for this study. Use the checklist to confirm a patient's eligibility. For each patient, this checklist must be photocopied, completed and maintained in the patient's chart.

In calculating days of tests and measurements, the day a test or measurement is done is considered Day 0. Therefore, if a test is done on a Monday, the Monday four weeks later would be considered Day 28.

PrECOG Patient No. _____

Patient's Initials (F, M, L) _____

Physician Signature and Date _____

NOTE: PrECOG does not allow waivers to any protocol specified criteria. All eligibility criteria listed in Section 3 must be met, without exception. The registration of individuals who do not meet all criteria listed in Section 3 can result in the participant being censored from the analysis of the study, and a major protocol violation. All questions regarding clarification of eligibility criteria must be directed to the Medical Monitor or PrECOG Study Contact.

NOTE: Institutions may use the eligibility checklist as source documentation if it has been reviewed, signed, and dated prior to registration by the treating physician.

_____ 3.1 Patients must have histologically confirmed MIBC (T2-T4a, N0-N1, M0 per American Joint Commission on Cancer [AJCC]) pure or mixed histology urothelial carcinoma [urothelial carcinoma should be the dominant histology]. Clinical node-positive (N1) patients are eligible provided the lymph nodes (LNs) are confined to the true pelvis and are within the planned surgical LN dissection template.

Staging: _____

_____ 3.2 The most recent TURBT that showed muscularis propria invasion should be within 10 weeks prior to beginning study therapy. Patients must have sufficient baseline tumor tissue from either initial or repeat TURBTs. **The local site pathologist will be asked to estimate and record the rough approximate percentage of viable tumor in the TURBT sample (initial or repeat TURBT with highest tumor content) to document at least 20% viable tumor content prior to registration.** This is to ensure adequate tissue is available to perform tumor infiltrating CD8+ T-cell assessment. (The actual CD8+ T-analysis will be done by a Central Laboratory and will not be done prior to registration.)

_____ 3.3 Patients must be ineligible for cisplatin-based chemotherapy due to any of the following below **OR** refused cisplatin-based chemotherapy:

- Creatinine clearance(CrCl) <60 mL/min (with ECOG Performance Status (PS) 0-1 [Appendix I])

CrCl _____ mL/min ECOG PS _____ NA

- Creatinine clearance(CrCl) ≥ 60 mL/min with ECOG PS 2 (if patient fit for RC)

CrCl _____ mL/min ECOG PS _____ NA

- Hearing impaired ≥ Grade 2 by CTCAE criteria

Yes No

- Neuropathy ≥ Grade 2 by CTCAE criteria

Yes No

Patient refused cisplatin-based chemotherapy? Yes N/A (see above)

-
- _____ 3.4 Patients must be medically fit for TURBT and radical cystectomy (RC).
- _____ 3.5 Age \geq 18 years.
- _____ 3.6 Ability to understand and willingness to sign IRB-approved informed consent.
- _____ 3.7 Willing to provide tumor tissue, blood, and urine samples for research (Section 14).
- _____ 3.8 Adequate organ function as measured by the following criteria, obtained \leq 4 weeks prior to registration:
- Absolute Neutrophil Count (ANC) \geq 1000/mm³ (stable off growth factor within 4 weeks of first study drug administration)
ANC: _____ Date of Test: _____
 - Platelets \geq 100,000/mm³
Platelets: _____ Date of Test: _____
 - Hemoglobin \geq 8 g/dL
Hemoglobin: _____ Date of Test: _____
 - Serum Creatinine Clearance \geq 30 mL/min using the Cockcroft-Gault formula (Appendix II)
CrCL: _____ Date of Test: _____
 - ALT and AST \leq 2.5x ULN
ALT: _____ Institution ULN: _____ Date of Test: _____
AST: _____ Institution ULN: _____ Date of Test: _____
 - Total Bilirubin \leq 1.5x ULN (in the absence of previously diagnosed Gilbert's disease)
Total Bilirubin: _____ ULN: _____ Date of Test: _____
- _____ 3.9 Women must not be pregnant or breastfeeding since we do not know the effects of nivolumab and lirilumab on the fetus or breastfeeding child. All sexually active females of childbearing potential (not surgically sterilized and between menarche and 1 year post menopause) must have a blood test to rule out pregnancy within 4 weeks prior to registration.
- Is the patient a woman of childbearing potential? _____ (yes/no)
- If yes, Date of Test: _____ Results: _____
- _____ 3.10 Sexually active women of child-bearing potential with a non-sterilized male partner and sexually active men must agree to use 2 methods of adequate contraception (hormonal plus barrier or 2 barrier forms) OR abstinence prior to study entry, for the duration of study participation, and for 5 months for women and 7 months for men following last dose of study drugs. Method of contraception must be documented.
- NOTE:** Should a woman become pregnant or suspect she is pregnant while participating in this study, she should inform her treating physician immediately.
- _____ 3.11 Patients may not have active or prior documented autoimmune disease within the past 2 years prior to Screening or other immunosuppressive agent within 14 days of study treatment.
- NOTE:** Patients with well controlled type 1 diabetes mellitus, vitiligo, Graves disease, Hashimoto's disease, eczema, lichen simplex chronicus, or psoriasis not requiring systemic treatment (within the past 2 years prior to Screening) are not excluded.
-

-
- _____ 3.12 Patients may not have locally advanced unresectable or metastatic urothelial carcinoma as assessed on baseline radiographic imaging obtained within 28 days prior to study registration. The required radiographic imaging includes: Chest/Abdomen/Pelvis CT with or without contrast. CT with contrast is the preferred method unless otherwise contraindicated due to allergy, impaired renal function, etc. (MRI is allowed as alternative).
- _____ 3.13 Patients may not have concurrent upper urinary tract (i.e. ureter, renal pelvis) invasive urothelial carcinoma. Patients with history of non-invasive (Ta, Tis) upper tract urothelial carcinoma that has been definitively treated with at least one post-treatment disease assessment (i.e. cytology, biopsy, imaging) that demonstrates no evidence of residual disease are eligible.
- _____ 3.14 Patients may not have another malignancy that could interfere with the evaluation of safety or efficacy of the study drugs. Patients with a prior malignancy will be allowed without study chair approval in the following circumstances:
- Not currently active and diagnosed at least 3 years prior to the date of registration.
 - Non-invasive diseases such as low risk cervical cancer or any cancer *in situ*.
 - Localized (early stage) cancer treated with curative intent (without evidence of recurrence and intent for further therapy), and in which no systemic chemotherapy was indicated (e.g. low/intermediate risk prostate cancer, etc.). Patients with other malignancies not meeting these criteria must be discussed with PrECOG prior to registration.
- _____ 3.15 Patients may not have received any prior immune checkpoint inhibitor (i.e. anti-KIR, anti-PD-1, anti-PD-L1, or other).
- _____ 3.16 Patients may not have undergone major surgery (e.g. intra-thoracic, intra-abdominal or intra-pelvic), open biopsy or significant traumatic injury or specific anti-cancer treatment ≤ 4 weeks prior to starting study drug, or patients who have had percutaneous biopsies or placement of vascular access device ≤ 1 week prior to starting study drug, or who have not recovered from side effects of such procedure or injury.
- _____ 3.17 Patients must not have clinically significant cardiac diseases, including any of the following:
- History or presence of serious uncontrolled ventricular arrhythmias.
 - Clinically significant resting bradycardia.
 - Any of the following within 3 months prior to starting study drug: myocardial infarction (MI), severe/unstable angina, Coronary Artery Bypass Graft (CABG), Congestive Heart Failure (CHF), Cerebrovascular Accident (CVA), Transient Ischemic Attack (TIA).
 - Uncontrolled hypertension defined by a SBP ≥ 160 mm Hg and/or DBP ≥ 100 mm Hg, with or without anti-hypertensive medication(s).
- _____ 3.18 Patients may not have chronic active liver disease or evidence of acute or chronic Hepatitis B Virus (HBV) or Hepatitis C (HCV).
- _____ 3.19 Patients may not have known diagnosis of human immunodeficiency virus (HIV) infection. Testing is not required in absence of clinical suspicion.
- _____ 3.20 Patients may not have known diagnosis of any condition (e.g. post-hematopoietic or solid visceral organ transplant, pneumonitis, inflammatory bowel disease, etc.) that requires chronic immunosuppressive therapy. Usage of non-steroidal anti-inflammatory medications (NSAIDs) for the treatment of osteoarthritis and uric acid synthesis inhibitors for the treatment of gout are permitted. For questions, please consult PrECOG.
-

- _____ 3.21 Patients with any serious and/or uncontrolled concurrent medical conditions (e.g. active or uncontrolled infection, uncontrolled diabetes) or psychiatric illness that could, in the investigator's opinion, cause unacceptable safety risks or potentially interfere with the completion of the treatment according to the protocol are not eligible.
- _____ 3.22 Patients may not have any live viral vaccine used for prevention of infectious diseases within 4 weeks prior to study drug(s).
- _____ 3.23 Patients unwilling or unable to comply with the protocol.
- _____ 3.24 Patients with a known allergy to any of the study medications, their analogues, or excipients in the various formulations of any agent are not eligible.
- _____ 3.25 Patients may not participate in any other therapeutic clinical trials, including those with other investigational agents not included in this trial throughout the duration of this study.

4. Registration Procedures

4.1 Ethics

This study will be conducted in accordance with the ethical principles that have their origin in the current Declaration of Helsinki and will be consistent with applicable US regulatory requirements and International Conference on Harmonization/Good Clinical Practice (ICH/GCP).

The study will be conducted in compliance with the protocol. The protocol and any amendments and the patient informed consent will receive Institutional Review Board (IRB) approval prior to initiation of the study.

Freely given written informed consent must be obtained from every patient or their legally authorized representative prior to clinical trial participation, including informed consent for any screening procedures conducted to establish patient eligibility for the trial.

Study personnel involved in conducting this trial will be qualified by education, training, and experience to perform their respective task(s). This trial will not use the services of investigators or study personnel where sanctions have been invoked or where there has been scientific misconduct or fraud (e.g., loss of medical licensure, debarment). Investigators are responsible for the conduct of the study at their study site.

4.2 Regulatory Requirements

Before a site may enter patients, protocol-specific regulatory and other documents must be submitted to PrECOG as noted in study materials. Detailed information regarding document submission and control is provided to each site in separate study materials.

Once required documents are received, reviewed, and approved by PrECOG or their representative, a Study Reference Manual (SRM) will be forwarded to the site. Any changes to site regulatory documents must be submitted by the investigator to the responsible party in a timely manner. Initial study drug shipment will not occur until the regulatory packet is complete. No patients will begin protocol therapy without formal registration as per the process below.

4.3 Phase Ib Patient Registration

Patients must not start protocol treatment prior to registration.

Patients must meet all of the eligibility requirements listed in Section 3 prior to registration.

An eligibility checklist is included in Section 3. A confirmation of eligibility assessment by the investigator and/or site will be performed during the registration process.

Upon determination that a subject meets eligibility criteria, the subject will be registered in the study by site personnel via an electronic data capture (eDC) system.

NOTE: The local site pathologist will be asked to estimate and record the rough approximate percentage of viable tumor in the TURBT sample (initial or repeat TURBT with highest tumor content) to document at least 20% viable tumor content prior to registration. This is to ensure adequate tissue is available to perform tumor infiltrating CD8+ T-cell assessment. (The actual CD8+ T-analysis will be done by a Central Laboratory and will not be done prior to registration.)

Neoadjuvant treatment should begin ≤ 10 working days from date of registration. Please note neoadjuvant treatment must also start within 10 weeks of the most recent TURBT that showed muscularis propria invasion.

Full information regarding registration procedures and guidelines can be found in the SRM provided to your site. Correspondence regarding patient registration must be kept in the study records.

4.4 Research Tissue, Blood, and Urine Samples

Mandatory tumor tissue samples are required at baseline and from radical cystectomy.

Mandatory peripheral blood and urine samples will also be collected.

Time points for tissue, blood, and urine samples are outlined in the study parameters (Section 11) and specific requirements are outlined in the correlative section of this protocol (Section 14) and the lab manual.

5. Study Design

This is a Phase Ib open-label clinical trial for patients that are either cisplatin-ineligible or refuse cisplatin-based chemotherapy and have MIBC (T2-T4a, N0-N1, M0). Patients will be sequentially enrolled first into Cohort 1 treated with nivolumab alone (N=12). In the absence of the occurrence of high rate of treatment related AEs as defined in Section 5.4 and 13.1.1 with neoadjuvant nivolumab treatment, the study will proceed with enrollment into Cohort 2 of neoadjuvant treatment with combination nivolumab/lirilumab. (In both cohorts, neoadjuvant treatment must start within 10 weeks of transurethral resection of the most recent TURBT that showed muscularis propria invasion). Each group will receive a total of 4 weeks (week 0 and 4) of neoadjuvant therapy followed by radical cystectomy (RC) with bilateral (standard or extended) pelvic lymph node dissection (PLND).

The RC with bilateral (standard or extended) PLND will occur as soon as possible but within 6 weeks after the last neoadjuvant dose in either cohort.

5.1 Number of Patients

The study will aim to screen 43 eligible patients in order to enroll 36 patients in the trial (assuming about 20% tumor tissue assessment screen failure rate). Estimate at least 2-3 patients per month at approximately 8 sites. The estimated time for accrual completion will be approximately 18 months.

5.2 Replacement of Patients

A patient will be replaced if following TURBT and registration into the study, they do not meet any of the following criteria:

- Begin neoadjuvant therapy within 10 weeks of the most recent TURBT that showed muscularis propria invasion
- Receive at least one study treatment dose (nivolumab alone or nivolumab and lirilumab)
- Adequate (at least 20%) viable tumor content in any TURBT

5.3 Expected Duration of Treatment and Patient Participation

Following registration, patients in each group will receive a total of 4 weeks of neoadjuvant therapy followed by RC with bilateral (standard or extended) PLND as soon as possible but within 6 weeks of the completion of neoadjuvant therapy.

Off treatment visit will occur approximately 30 days following cystectomy (if cystectomy is not performed, Off Treatment visit should be performed at next scheduled appointment or treating physician discretion, as clinically indicated) and patients will be followed for 100 days after neoadjuvant treatment for AEs. Adverse events may be reviewed at the next visit ≥ 100 days after last dose of neoadjuvant therapy or phone follow-up may be done to review adverse events.

Patients will be followed clinically and radiographically for at least 2 years post-cystectomy or when study-wide follow-up ends per standard of care. Date of diagnosis for progression, first subsequent therapy and survival shall be reported. Phone follow-up may also be done for patients unable or unwilling to return for follow-up evaluations.

5.4 Interim Safety Analysis

After 6 and 12 patients on Cohort 1 and 6 patients on Cohort 2 complete surgery, the study will be monitored for nivolumab or nivolumab/lirilumab treatment-related toxicities as noted below.

- Any Grade hypophysitis, meningitis, or immune-related neurologic AEs

- Grade 2 or higher myocarditis
- Persistent Grade 2 immunologic AEs (such as colitis, pneumonitis, and nephritis) that do not recover to Grade 1 or resolve within 6 weeks after the last dose of study drug (Exceptions: rash, fatigue, amylase/lipase elevations, other electrolyte abnormalities).
- Grade 3 or higher immunologic AEs such as uveitis, pericarditis, hepatitis, colitis/diarrhea, nephritis, pancreatitis, myositis, endocrine, rash, etc., except Grade 3 hypothyroidism or Grade 3 infusion reaction.
- Grade 4 non immunologic AEs, as well as Grade 4 hypothyroidism or Grade 4 infusion reaction.

There will be no suspension to accrual after the first 6 patients in each cohort. Also, accrual will start on Cohort 2 once accrual to Cohort 1 is complete (unless needed based on toxicity noted).

If 3 or more of these 6 patients on a single cohort experience nivolumab or nivolumab/lirilumab treatment-related adverse events as noted above, the study will be suspended for a safety review.

6. Treatment Plan

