10.1 Evaluable Population Definitions

Evaluable for Toxicity: All patients will be evaluable for toxicity from the time of their first treatment with nivolumab and/or lirilumab.

Evaluable for Tumor Response: Only those patients who have received at least one dose of therapy, and undergo radical cystectomy will be considered evaluable for tumor response. These patients will have their tumor response classified according to the definitions stated below. (**NOTE:** Patients who exhibit objective disease progression prior to the end of treatment will also be considered evaluable.)

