13.1.1 Interim Safety Analysis (Primary Endpoint)

Treatment-related toxicities as noted below related to nivolumab or nivolumab/lirilumab will be monitored in each cohort of the study separately after 6 and 12 patients in Cohort 1 and 6 patients in Cohort 2 have completed surgery. There will be no suspension to accrual.

- Any Grade hypophysitis, meningitis, or immune-related neurologic AEs
- Grade 2 or higher myocarditis
- Persistent Grade 2 immunologic AEs (such as colitis, pneumonitis, and nephritis) that do not recover to Grade 1 or resolve within 6 weeks after the last dose of study drug (Exceptions: rash, fatigue, amylase/lipase elevations, other electrolyte abnormalities).
- Grade 3 or higher immunologic AEs such as uveitis, pericarditis, hepatitis, colitis/diarrhea, nephritis, pancreatitis, myositis, endocrine, rash, etc., except for Grade 3 hypothyroidism, Grade 3 pruritus or Grade 3 infusion reaction.
- Grade 4 non immunologic AEs, as well as Grade 4 hypothyroidism or Grade 4 infusion reaction.

If 3 or more of these 6 patients on a single cohort experience treatment-related adverse events as noted above related to nivolumab or nivolumab/lirilumab, the study will be suspended for a safety review. The following table gives the probabilities of stopping given various probabilities of toxicity.

True but unknown probability of immunologic toxicity	0.17	0.25	0.33	0.42	0.5
Probability of suspension	0.06	0.17	0.32	0.49	0.66

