#### **7.8. Interim Analysis**

There will be 3 interim safety analyses in this study. After 6 and 12 patients on Cohort 1 and 6 patients on Cohort 2 complete surgery, the study will be monitored for nivolumab or nivolumab/lirilumab treatment-related toxicities as noted below.

- Any Grade hypophysitis, meningitis, or immune-related neurologic AEs
- Grade 2 or higher myocarditis
- Persistent Grade 2 immunologic AEs (such as colitis, pneumonitis, and nephritis) that do not recover to Grade 1 or resolve within 6 weeks after the last dose of study drug (Exceptions: rash, fatigue, amylase/lipase elevations, other electrolyte abnormalities).
- Grade 3 or higher immunologic AEs such as uveitis, pericarditis, hepatitis, colitis/diarrhea, nephritis, pancreatitis, myositis, endocrine, rash, etc., except Grade 3 hypothyroidism or Grade 3 infusion reaction.
- Grade 4 non immunologic AEs, as well as Grade 4 hypothyroidism or Grade 4 infusion reaction.

The first interim safety analysis will be performed as soon as the 6th patient in cohort 1 complete radical cystectomy (RC) surgery. A treatment-related AE by toxicity grade and SOC summary tables will be provided to clinical team review to determine whether 3 or more patients meet above specified AEs. If 3 or more patients are identified, the study will be suspended for a safety review.

An AE listing will also be provided for clinical team review.

The 2nd interim safety analysis will be performed as soon as the 12th patient in cohort 1 complete RC surgery. The same AE analysis as the first interim analysis will be performed for the all 12 patients. If 6 or more patients experience above specified AEs, the study will be suspended for a safety review.

The 3rd interim safety analysis will be performed as soon as the 6th patient in cohort 2 complete RC surgery. The same AE analysis will be repeated for the all 18 patients. If 9 or more patients experience above specified AEs, the study will be suspended for a safety review.

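### The safety looks are triggered by completed cystectomies and, on the plain reading, count only those patients, so toxicity that prevents surgery may escape the 3-of-6 suspension rule

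*Protocol*

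**What the plan says.** Protocol 5.4 sets the timing: "After 6 and 12 patients on Cohort 1 and 6 patients on Cohort 2 complete surgery, the study will be monitored". Section 13.1.1 repeats it: "after 6 and 12 patients in Cohort 1 and 6 patients in Cohort 2 have completed surgery". Both sections then give the suspension criterion: "If 3 or more of these 6 patients on a single cohort experience" one of the listed treatment-related events, the study is suspended for a safety review. Accrual does not pause for the looks.

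SAP 7.8 ties its three looks to the 6th and 12th cystectomy in Cohort 1 and the 6th in Cohort 2, each run as soon as that operation is done. It asks for 3 or more patients at the first look (no denominator given), 6 or more among all 12 at the second, and 9 or more among all 18, pooled over cohorts, at the third. One listed event is "Persistent Grade 2 immunologic AEs (such as colitis, pneumonitis, and nephritis) that do not recover to Grade 1 or resolve within 6 weeks" of the last dose.

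The protocol expects that toxicity will sometimes prevent surgery. A secondary objective is "To describe the rate of patients in each cohort who do not get RC within 6 weeks after completion of neoadjuvant treatment" because of treatment-related adverse events, and section 5.3 provides an Off Treatment visit for patients without cystectomy. For safety in general, section 10.1 states: "All patients will be evaluable for toxicity from the time of their first treatment with nivolumab and/or lirilumab". Section 8.3 and SAP 7.5.1 likewise include everyone given at least one dose.

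**The concern.** Reaching surgery is partly a consequence of the toxicity being monitored. If the six are the patients who completed surgery, a treated patient who dies, or is too ill for cystectomy, is in neither the numerator nor the denominator, and that patient's course does not advance the look. The rule would be least sensitive when toxicity is bad enough to cost patients a curative operation. The printed suspension probabilities would also not describe the rule as it operates in treated patients.

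There is a smaller timing gap. Surgery is to follow promptly and at the latest 6 weeks after the last dose, while the persistent Grade 2 item needs the full 6 weeks. For a patient operated on earlier, that item cannot yet be scored when the look is run.

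**Working it through.** **Inputs.** From protocol 13.1.1: the rule of 3 or more among 6; the row "True but unknown probability of immunologic toxicity" with 0.17, 0.25, 0.33, 0.42, 0.5; and the row "Probability of suspension" with 0.06, 0.17, 0.32, 0.49, 0.66. From the synopsis: Cohort 1 has 12 eligible, treated patients. From 5.2: patients are replaced for a late start, no dose received or inadequate tissue, but not for missed cystectomy. Not in the documents: q, the share of patients with a listed toxicity who never reach surgery. I take q = 0.10, 0.25 and 0.50.

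**Step 1: reproduce the table.** With X ~ Bin(6, p), P(X ≥ 3) at p = 1/6, 1/4, 1/3, 5/12, 1/2 is 0.062, 0.169, 0.320, 0.490, 0.656. To two decimals this is the printed row. The table therefore assumes six patients whose inclusion does not depend on toxicity.

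**Step 2: count only patients who have surgery.** If all patients without a listed toxicity reach surgery, the toxicity rate among those operated on is

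p_obs = p(1 − q) / (1 − pq).

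For p = 0.50 and q = 0.25: 0.375 / 0.875 = 0.429, and P(X ≥ 3) with X ~ Bin(6, 0.429) is 0.51. Over the range:

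| Assumed q | p = 1/6 | p = 1/4 | p = 1/3 | p = 5/12 | p = 1/2 |
|---|---|---|---|---|---|
| 0 (printed) | 0.06 | 0.17 | 0.32 | 0.49 | 0.66 |
| 0.10 | 0.05 | 0.14 | 0.28 | 0.44 | 0.61 |
| 0.25 | 0.03 | 0.10 | 0.21 | 0.35 | 0.51 |
| 0.50 | 0.01 | 0.04 | 0.10 | 0.19 | 0.32 |

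**Step 3: let patients without a listed toxicity miss surgery too.** If a share r of them does, p_obs = p(1 − q) / [p(1 − q) + (1 − p)(1 − r)]. When q = r, p_obs = p and nothing is lost. With r = 0.10 and p = 0.50, suspension is 0.57 at q = 0.25 and 0.37 at q = 0.50. The loss comes only from missed surgery that is related to toxicity.

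**Step 4: the 12-surgery look.** With 12 treated patients and no replacement for missed surgery, this look is reached only if all 12 are operated on. If a share m misses surgery for any reason, the probability is (1 − m)^12: 0.54, 0.28 or 0.14 for assumed m = 5%, 10% or 15%.

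**Step 5: the looser reading.** Suppose surgery sets only the timing and every patient treated so far is counted against the threshold of 3. At p = 1/3, suspension is then 0.43 with 7 treated and 0.53 with 8, not the printed 0.32. The table fits this reading no better.

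**The case against.** The strongest reply is that surgery is only the clock. Between the trigger and the rule, section 5.4 also speaks of the first 6 patients in each cohort, with no surgery condition, and the rule's back-reference could point there. Protocol 13.1 and SAP 7.1 refer to the first 12 patients in the same way. The SAP states that it supersedes the protocol's statistical considerations; it sets safety analysis on all treated patients (7.5.1, 7.6) and names no denominator at the first look. This stands as a real ambiguity, so exclusion cannot be called the settled rule. It does not remove the problem. In 13.1.1 the only six patients per cohort are those who have completed surgery, the SAP's 12 and 18 equal the running counts of completed operations, and no section says how a treated patient without surgery enters a look.

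A reader might go further and infer that the worst cases disappear from safety oversight, or that the primary safety estimate is biased. The documents do not support that. SAEs are reported within 24 hours, all deaths within 100 days of the last dose are collected, and the primary rate is estimated in every treated patient. Sections 8.3 and 10.1 define analysis populations, so they are not contradicted by an interim check on a different set. Nor can a later, fitter patient always fill the gap: at the 12-patient look no thirteenth patient is planned, and the look would simply not be reached.

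The size is also open to challenge. It rests on an assumed q, and a patient with a listed event who still has surgery, even late, is counted. The one combination figure in the protocol, 15% Grade 3–4 treatment-related events (section 1.6), comes from another tumor type and uses a different event definition. A rate near that lies close to the lowest column, where the absolute change is small and fewer suspensions are not in themselves a harm. The timing gap is narrower than it looks, because the SAP re-examines Cohort 1 patients at later looks; only the last look has none after it.

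**Conclusion.** The concern holds as a defect in how the interim rule is specified. All three sections trigger the looks by completed surgery, and 13.1.1 on its plain reading restricts the count to those patients. The printed probabilities are correct arithmetic, but for six patients unselected by toxicity.

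Under the assumption that only patients with a listed toxicity miss surgery, shares of 10%, 25% and 50% lower suspension from 0.66 to 0.61, 0.51 and 0.32 at p = 0.50, from 0.32 to 0.28, 0.21 and 0.10 at p = 1/3, and from 0.06 to 0.05, 0.03 and 0.01 at p = 1/6. If missed surgery is unrelated to toxicity, the count loses nothing, though a look can still be delayed or, for the 12-surgery look, not reached. The weakness is confined to the formal suspension rule.

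**What to change.** Use one definition of the look set in protocol 5.4, protocol 13.1.1 and SAP 7.8, for example:

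> Each look covers the first 6 (in Cohort 1 also the first 12) patients of the cohort who received study treatment. A patient is ready for the look at the earliest of cystectomy, the end of the existing 6-week surgical window after the last dose, a recorded decision not to proceed to surgery, or death. Listed events count whether or not surgery took place. The persistent Grade 2 item is updated for each patient once 6 weeks have passed since the last dose; the look does not wait for it.

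The surgical window gives every patient a latest date, so a look cannot stay open indefinitely. The event list need not change for this purpose. With this set, the printed table applies to a 3-of-6 rule in each cohort.

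The protocol's per-cohort 3-of-6 rule and the SAP's 6-of-12 and pooled 9-of-18 thresholds must also be reconciled, and suspension probabilities given for whichever thresholds are kept; the printed table covers only 3 of 6. Protocol 6.1 and 12.1.5 indicate that Cohort 2 dosing has begun, so the change should apply to the looks still to come.

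The cost is wording in two protocol sections and one SAP section, with no new data. The persistent Grade 2 item may become final a few weeks after a look, and suspension becomes somewhat more likely when toxicity blocks surgery.
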